#### **6.7.5. Multiple Assessments**

Once analysis windows are assigned, a patient's individual analysis window could potentially contain more than one visit. Records from all visits, including scheduled, unscheduled and early discontinuation visits could be flagged as the "analyzed record" within the analysis window, although the records from scheduled visit will take priority.

For measurement taken prior to the first dose of study drug, in the event of multiple visits falling within an analysis window, the following rule will be used to determine the "analyzed record":

- The record closest to, but prior to the first dose of study drug should be selected as the baseline "analyzed record." This could include scheduled visits and other screening visits.

For post baseline visits, measurements taken during the 24-week double-blind, placebo-controlled period will be included only in the analysis windows up to Week 24. Measurements taken after patients transition to the active drug period will be included only in the analysis windows after Week 24. Once patients transition to the active drug period, all measurements collected on or after the transition date will not be included in the analysis windows for the first 24 weeks double-blind placebo-controlled period. Furthermore, in the event of multiple visits falling within an analysis window, the following rules will be used in sequence to determine the "analyzed record" for the analysis window:

- If a scheduled visit occurred during the analysis window, then the measurement taken from the scheduled visit will be used.
- If no scheduled visit occurred during the analysis window, the measurement taken closest to the scheduled day will be used as the "analyzed record."
- If no scheduled visit occurred during the analysis window and there is a tie between unscheduled visits in the number of days before and after the scheduled day, measurements from the later visit will be used as the "analyzed record."

For all analyses, only the “analyzed record” within each analysis window will be summarized in a table. If there are other visit records within the analysis window, they will only be included in data listings. In addition, composite scores (eg, ALSFRS-R total score or muscle strength mega score) will be calculated based on the “analyzed record.”

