### **6.7.4. Analysis Windows**

Since study visits do not always take place exactly as scheduled per protocol, it is necessary to assign the actual observation dates to analysis windows for analysis purposes.

For measurement taken prior to the first dose of study drug, the analysis window is defined as the interval of time prior to the first dose of study drug. Measurements taken on or after the first dose of study drug will be assigned to the next scheduled analysis window.

For data collected at a scheduled post baseline visit, the analysis window will be assigned based on the scheduled study day of the nominal visit as collected on the eCRF.

For unscheduled post baseline visits, early discontinuation visit or follow-up visit, measurements taken on or after the first dose of study drug will be assigned to an analysis window using defined lower and upper bounds for each analysis window. Measurements assigned in an analysis window will have study day greater than or equal to the lower bound but no greater than the upper bound of the analysis window. The lower bound and the upper bound for the analysis windows are defined as the midpoints of the scheduled visits for all assessments (see [Section 12.3](#)).

Visits are identified as the nominal visits according to the eCRFs. Each visit will be identified with the visit descriptor (eg, "Week 24"). If a patient has two or more study visits in one analysis window, one record will be flagged as the "analyzed record" for that analysis window.

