### 12.3. Analysis Windows

Measurements collected during the 24-week double-blind placebo-controlled period will be included only in the analysis windows up to Week 24; measurements collected after patients transition to the active drug period will be included only in the analysis windows after Week 24.

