**Table 11: Analysis Windows for EQ-5D-5L, EQ-VAS and ALSAQ-40**

Visit	Scheduled Day	Lower Bound	Upper Bound
Screening	<1	<1	<1
Day 1	1	1	1
Week 12	85	2	126
Week 24	169	127	210
Week 36	253	211	294
Week 48	337	295	350
Follow-up	365	351	>351

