**Table 13: Analysis Windows for ECG**

Visit	Scheduled Day	Lower Bound	Upper Bound
Screening	<1	<1	<1
Day 1	1	1	1
Week 24	169	2	252
Week 48	337	253	350
Follow-up	365	351	>351

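### Early-discontinuation and other day-windowed records from the start of the active drug period have no permitted analysis window, so by-visit safety tables and exploratory post-Week 24 models lose them

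*SAP*

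**What the plan says.** Scheduled visits go to windows by their nominal visit (SAP 6.7.4). Early-discontinuation, unscheduled and follow-up visits go by study day against each window's bounds, and the bounds are strict: "Measurements assigned in an analysis window will have study day greater than or equal to the lower bound but no greater than the upper bound". They are built by one rule: "The lower bound and the upper bound for the analysis windows are defined as the midpoints of the scheduled visits for all assessments".

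SAP 6.7.5 then separates the two study periods: "Measurements taken after patients transition to the active drug period will be included only in the analysis windows after Week 24". It also bars anything measured on the switch date or later from the double-blind windows. The head of SAP 12.3 repeats the condition: "measurements collected after patients transition to the active drug period will be included only in the analysis windows after Week 24". Section 6.7.5 also limits tables to the one analyzed record in each window; any other record is only listed.

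The Week 24 window ends on day 182 in Table 9 (ALSFRS-R, remote FVC, equipment use), 210 in Tables 10 and 11 (clinic FVC, grip and muscle strength, BDI-FS, vital signs, weight; EQ-5D-5L, EQ-VAS, ALSAQ-40), 266 in Table 12 (neurological exam), 252 in Table 13 (ECG) and 175 in Table 15 (safety laboratory). In each table the next window opens the following day.

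**The concern.** An early-discontinuation visit soon after the switch falls, by its study day, in the Week 24 window. The period rule excludes it from there, and the day bounds exclude it from the next window. No sentence moves it forward.

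The protocol's Schedule of Activities puts the early-discontinuation visit in the Week 48 column, so it carries ALSFRS-R, FVC, grip, HHD, ALSAQ-40, EQ-5D-5L, BDI-FS, vital signs, ECG and laboratory tests. For delayed-start patients the hole covers roughly the first 6 weeks on reldesemtiv, and 12 weeks for ECG. By-visit summaries then miss values from patients who stop early. Week 48 models for ALSFRS-R, FVC and grip lose what may be a patient's only active-period value. For ALSFRS-R this contradicts SAP 8.8.2, which promises that the delayed-start comparisons use everything gathered through Week 48.

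The hole can also swap an on-drug value for an off-drug one. If the last dose and early-discontinuation visit are on day 200 and follow-up is 28 days later on day 228, the day-200 vital signs have no window, while the day-228 values become the Week 36 record.

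**Working it through.** **Inputs.** Scheduled days and bounds: SAP Tables 9 to 13 and 15. Switch: Week 24 visit at 168 ± 4 days (Protocol Table 3). Under the study-day rule in SAP 6.7.2 this is day 169, range 165 to 173.

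**Step 1: reproduce the printed bounds.** The lower bound of the next window is the midpoint of the two scheduled days; Week 24 ends the day before.

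| SAP table | Midpoint | Week 24 ends | Next window |
|---|---|---|---|
| 9 | (169+197)/2 = 183 | 182 | Week 28 |
| 10, 11 | (169+253)/2 = 211 | 210 | Week 36 |
| 12 | (169+365)/2 = 267 | 266 | Follow-up |
| 13 | (169+337)/2 = 253 | 252 | Week 48 |
| 15 | (169+183)/2 = 176 | 175 | Week 26 |

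All agree with the SAP, so the bounds are not misprints.

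**Step 2: count post-switch days with no permitted window.** Days = Week 24 upper bound − switch day. The brackets show a switch on day 173 to day 165.

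| SAP table | Empty days | Number | Share of 168 days |
|---|---|---|---|
| 9 | 170-182 | 13 (9-17) | 8% |
| 10, 11 | 170-210 | 41 (37-45) | 24% |
| 12 | 170-266 | 97 (93-101) | 58% |
| 13 | 170-252 | 83 (79-87) | 49% |
| 15 | 170-175 | 6 (2-10) | 4% |

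**Step 3: upper bound on patients.** The documents give no active-period dropout rate. Assumption: the planned double-blind loss, 1 − 444/555 = 20%, recurs evenly over 168 days among 444 entrants, which is 444 × 0.20 = 88.8 leavers.

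- FVC, grip, ALSAQ-40, vital signs: 88.8 × 41/168 = 21.7
- ECG: 88.8 × 83/168 = 43.9
- ALSFRS-R: 88.8 × 13/168 = 6.9

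These cover both arms. Under 2:1 randomization the delayed-start third is 7.2, 14.6 and 2.3. With 10% loss, every figure halves.

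**Step 4: does another reading save the record?** If the day bounds overrode the period rule, the value would enter the Week 24 window, where the scheduled Week 24 visit takes priority (SAP 6.7.5), so it would normally still be listed only. The sentence in 6.7.4 that sends measurements to the following window concerns timing relative to the first dose of study drug; early-discontinuation visits have their own rule in the same section.

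**The case against.** The strongest reply is that 6.7.5 and 12.3 are worded affirmatively, and 12.3 sets the condition at the head of the tables. A programmer could take it as an instruction to carry the record into the next window. That reading is possible, but it breaks the strict lower bounds of 6.7.4, and nothing in the SAP says which rule yields. The text still needs correcting.

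Other objections narrow the point, and they stand:

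- A reader might infer that active-period safety results would describe only patients who tolerated the drug. The documents do not support this. Adverse-event tables do not use the windows, and the abnormal-laboratory, vital-sign and ECG counts take any qualifying post-baseline value, with unscheduled and follow-up assessments included (SAP 9.2, 9.5 to 9.7).
- A reader might infer that these patients have nothing beyond the early-discontinuation visit. Protocol 7.2.1 encourages them to stay and offers continued visits or a follow-up visit 4 weeks after the last dose. Stopping on days 183-210 puts follow-up on days 211-238, inside Week 36 of Tables 10 and 11, though off drug.
- The counts in step 3 are ceilings. Protocol 7.2 exempts deaths, consent withdrawals and patients lost to follow-up from the early-discontinuation visit. Some visits will be remote, and Protocol 8.1 and 8.2 drop grip, HHD, vital signs and ECG when a clinic visit is converted to remote. A patient with a scheduled record in the next window loses nothing from that window.

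It is also fair to say that moving an early value to a distant nominal week blurs timing: a day-170 ECG would be labelled Week 48, scheduled for day 337. This is not decisive, because the SAP already accepts it after Day 1. The ECG Week 24 window and the ALSAQ-40 Week 12 window both open on day 2.

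**Conclusion.** The two rules conflict, and read literally they leave a range of post-switch days without a window in Tables 9 to 13 and 15. The loss falls on by-visit safety summaries and exploratory models after Week 24. The hole is short for laboratory tests (6 days) and ALSFRS-R (13 days), longer for FVC, grip, ALSAQ-40 and vital signs (41 days), and about half the active period for ECG (83 days).

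It would be wrong to infer a threat to the primary or secondary endpoints. They are all assessed at Week 24, where excluding post-switch data is intended and correct.

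The ceilings of about 22, 44 and 7 patients rest on the assumed 20% even loss and on every leaver having a complete early-discontinuation visit. The true numbers will be lower. The point is worth correcting before database lock because the change is cheap and the SAP's own commitment in 8.8.2 is otherwise not met for ALSFRS-R.

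**What to change.** In SAP 6.7.4 and 12.3, add a rule for patients who have entered the active drug period: the Week 24 window ends at the first active-period dose, and the first later window starts right after it. That window is Week 28 in Table 9, Week 36 in Tables 10 and 11, Follow-up in Table 12, Week 48 in Table 13 and Week 26 in Table 15. Its upper bound stays as printed. This removes every empty day and follows the convention already used after Day 1.

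Anchor the rule on the dose, not on a transition date. Protocol 4.1 has morning-visit patients take their first active dose on the day of the Week 24 visit, so a date-based cut-off is unclear for that day. Week 24 assessments done before that dose stay in Week 24.

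Also state that an early-discontinuation record takes priority over an off-drug follow-up record in the same window. Otherwise the closest-to-schedule rule in 6.7.5 picks follow-up: in the example above, day 228 is 25 days from the Week 36 target of day 253, and day 200 is 53 days away.

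The cost is a short text change, a footnote to the tables and window programming. The downside is that some early active-period values carry a later nominal week, which a table footnote should say.

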- nonalcoholic fatty liver disease including steatohepatitis
- nonhepatic causes (eg, rhabdomyolysis, hemolysis)

Patients who clearly meet the criteria for permanent discontinuation must never be re-challenged.

Additional Clinical Assessments and Observation

All patients in whom the study drug is permanently discontinued due to meeting the hepatic safety threshold as described above are to undergo a repeat test and a period of “close

observation” until abnormalities have stabilized and returned to normal (or returned to the patient’s baseline levels). Assessments that are to be performed during this period include:

- Retesting of AST, ALT, ALP, bilirubin (total and direct), and obtaining an INR within 48 hours
- In cases of TBL $>2 \times$ ULN or INR >1.5 , retesting of liver tests, bilirubin (total and direct), and INR within 48 hours

Confirmed abnormal liver function tests (LFTs) should be repeated 2-3 times weekly then weekly or less if abnormalities stabilize or the study drug has been discontinued and the patient is asymptomatic. Follow the patient and the laboratory tests (ALT, AST, TBL, INR) until all laboratory abnormalities return to baseline or normal.

- Initiate investigation of alternative causes for elevated AST or ALT and/or elevated TBL:
 - Obtain complete blood count (CBC) with differential to assess for eosinophilia
 - Obtain serum total immunoglobulin IgG, Anti-nuclear antibody (ANA), Anti Smooth Muscle Antibody, and Liver Kidney Microsomal antibody 1 (LKM1) to assess for autoimmune hepatitis
 - Obtain serum acetaminophen (paracetamol) levels
 - Obtain viral serologies
 - Obtain creatine phosphokinase, haptoglobin, lactate dehydrogenase, and peripheral blood smear
 - Perform appropriate liver imaging if clinically indicated
- Obtain a more detailed history of:
 - Prior and/or concurrent diseases or illness
 - Exposure to environmental and/or industrial chemical agents
 - Symptoms (if applicable) including right upper quadrant pain, hypersensitivity type reactions, fatigue, nausea, vomiting and fever
 - Prior and/or concurrent use of alcohol, recreational drugs and special diets
 - Concomitant use of medications (including non-prescription medicines and herbal and dietary supplements), plants, and mushrooms
- Obtain appropriate blood sampling for pharmacokinetics (PK) analysis if this has not already been collected
- Obtain hepatology consult (liver biopsy may be considered in consultation with an hepatologist)

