## 9.5. Routine Laboratory Data

Clinical chemistry, hematology and urinalysis laboratory measurements and value changes from baseline at each laboratory blood sample collection time point will be summarized. The count and percentage of patients who had normal or missing laboratory values at baseline and abnormal laboratory values post baseline will be presented. The lower limit of normal (LLN) and upper limit of normal (ULN) provided by the laboratories will be used as the criteria to determine abnormality. For each parameter, the denominator of the percentage will include patients with normal or missing assessments at baseline, and with at least one assessment post baseline. The numerator of the percentage will include patients who had at least one abnormal assessment post baseline among the patients that were counted in the denominator. Assessment collected at unscheduled visits or the Follow-up Visit will be included in the summary.

Shift of clinical laboratory results from baseline severity to the maximum post baseline severity will be presented for selected laboratory parameters. Clinical laboratory values will be also listed. Values outside the Laboratory's normal ranges and potentially clinically significant abnormal values will be flagged.

Estimated glomerular filtration rate (eGFR) will be calculated using the CKD-EPI cystatin equation ([Inker 2012](#)) and summarized as change from baseline, percentage change from

baseline, by categories (15 to <30, 30 to < 45, 45 to < 60, 60 to <90 and ≥90, as well as ≥10%, ≥25% and ≥= 50% decline from baseline) and by shift in categories.

Liver function test results will be summarized as change from baseline and as count and percentage of patients with normal baseline and abnormal post-baseline results in Alanine Aminotransferase (ALT), Aspartate Aminotransferase (AST), Alkaline Phosphatase (ALP) and bilirubin, with the following categories:

- ALT > 3xULN, > 5xULN, > 8xULN
- AST > 3xULN, > 5xULN, > 8xULN
- ALT and/or AST > 3xULN, > 5xULN, > 8xULN
- ALT and/or AST > 3xULN and total bilirubin > 2xULN and ALP < 2xULN
- ALT and/or AST > 3xULN and total bilirubin > 2xULN
- Bilirubin (total, indirect or direct) > 2xULN, >3xULN
- ALT or AST > 3 x ULN with symptoms including nausea, vomiting, anorexia, abdominal pain, fatigue, rash, dark-colored urine, light-colored bowel movements, jaundice, or fever

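### The one-record-per-window rule in SAP 6.7.5 conflicts with SAP 9.5 to 9.7 and, read literally, keeps repeat and unscheduled values out of the liver-threshold, eGFR and time-to-elevation outputs

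*SAP*

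**What the plan says.** SAP 6.7.5 sets the general rule. It opens with a reference to all analyses and continues that "only the “analyzed record” within each analysis window will be summarized in a table". The choice of record does not depend on its value: "If a scheduled visit occurred during the analysis window, then the measurement taken from the scheduled visit will be used". An unscheduled or early discontinuation record is used only when no scheduled visit falls in the window. The section then disposes of the rest: "If there are other visit records within the analysis window, they will only be included in data listings". Safety data are not exempted, and Table 15 in SAP 12.3 defines windows for the safety laboratory tests, so the rule reaches them.

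SAP 9.5 follows a different rule in its first paragraph. The numerator of the abnormal-laboratory table is "patients who had at least one abnormal assessment post baseline", and "Assessment collected at unscheduled visits or the Follow-up Visit will be included in the summary". SAP 9.6 and 9.7 carry equivalent sentences for vital signs and ECG.

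The later paragraphs of 9.5 list further outputs: "Shift of clinical laboratory results from baseline severity to the maximum post baseline severity will be presented for selected laboratory parameters"; eGFR by category, by percent decline and by shift; ALT, AST and bilirubin counts above multiples of ULN, alone and combined; and time to ALT, AST or bilirubin elevation. None of these says which records it uses.

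**The concern.** Two rules in the same SAP give different answers for the same kind of table. The exception is written where the authors wanted it, so a programmer could reasonably conclude that the general rule applies where it is absent. Those outputs are the ones that describe hepatic and renal severity.

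Repeat testing is part of how the protocol follows such events. Protocol 7.4 says: "Confirmed abnormal liver function tests (LFTs) should be repeated 2-3 times weekly then weekly or less if abnormalities stabilize". Protocol 7.3 lets the physician who reviews the renal results direct repeats up to 2-3 times a week, and Protocol 8 allows unscheduled samples for safety reasons. If those values are filtered out, a table meant to show how far a patient's values went shows instead where they stood at the scheduled visit. Both laboratory domains are adverse events of special interest.

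**Working it through.** The plan states no figure to reproduce. The check compares the texts and then asks which counts can move, and in which direction.

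**1. Which outputs have a stated exception**

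| Output | Unscheduled records stated as included? |
|---|---|
| Normal-to-abnormal laboratory counts (SAP 9.5, first paragraph) | Yes |
| Potentially clinically significant vital signs (9.6) and ECG (9.7) | Yes |
| Shift to maximum post-baseline severity (9.5) | Implied by the word maximum, not stated |
| eGFR categories, percent declines, shifts (9.5) | No; by-visit or worst value also not stated |
| ALT/AST/bilirubin threshold and combined rows (9.5) | No |
| Time to ALT/AST/bilirubin elevation (9.5) | No |

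**2. Direction.** Let A be all of a patient's post-baseline values in a period and S the subset kept by 6.7.5. Because S lies within A, max(S) ≤ max(A) for ALT, AST and bilirubin, min(S) ≥ min(A) for eGFR, and the first crossing time in S is no earlier than in A. A patient with any post-baseline record in a window keeps one, so denominators do not shrink to compensate. An ever-above-threshold count can fall or stay the same; it cannot rise.

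**3. How much a window can hold.** Table 15 gives Week 8 as days 43-70, which is 28 days. At 2-3 repeats a week that is 28/7 × 2 = 8 to 28/7 × 3 = 12 repeats, with one record tabulated. Week 26 is days 176-189, which is 14 days: 14/7 × 2 = 4 to 14/7 × 3 = 6. These are capacities if testing at that rate filled the window, not expected counts.

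**4. Which rows can move.** If a scheduled value above 3×ULN prompts the repeats, the patient is already in the >3× row and stays there. The rows that can change are those reached later:
- The scheduled ALT is between 5× and 8×ULN and a repeat exceeds 8×. Under 6.7.5 the patient is missing from the >8× row.
- The scheduled ALT exceeds 3× with bilirubin not above 2×, and a repeat shows both criteria met. The patient is missing from the combined row.

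Protocol 7.4 makes the first case possible. It makes a value between 5× and 8× a ground for permanent discontinuation if it lasts two weeks or more, or if the patient cannot keep to enhanced monitoring. Scheduled draws from Week 4 to Week 24 are 28 days apart (for example days 57 and 85), so two-week persistence cannot be judged without draws in between.

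**5. Which arm.** Protocol 2.3.1 reports ALT or AST above 3×ULN in the Phase 2 trial in 24 patients (7.0%) on reldesemtiv and 1 (0.9%) on placebo. With 555 randomized 2:1, the arms are 370 and 185. If the Phase 2 rates carried over, 0.070 × 370 = 25.9 and 0.009 × 185 = 1.7 patients would exceed 3×. Those rates pool all doses, including 450 mg twice daily, over 12 weeks. The figures indicate where liver repeats would concentrate. They do not count misclassified patients, because the >3× row is the one least affected.

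**The case against.** The strongest reply is that 9.5 is the specific laboratory section and should prevail. Its first paragraph includes unscheduled values. Its shift table is defined on the maximum. Its liver paragraph uses the same normal-at-baseline, abnormal-afterwards form as the table that has the exception. SAP 9.6 and 9.7 show that the authors' habit is to include unscheduled records. This is a fair account of the probable intent, and it disposes of one inference a reader might draw, that repeat values reach no table at all: 9.5 to 9.7 contradict that. It also makes the shift table a weak example, since a maximum reads naturally as taken over all records. It does not settle the other outputs, where the only text on record selection is the rule for all analyses.

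A second reply concerns repeat testing. In Protocol 7.4 the 48-hour retest and the frequent repeats stand under the follow-up of patients whose drug was stopped for meeting a hepatic threshold. An asymptomatic patient at 4×ULN with normal bilirubin and INR meets none of those criteria, so repeats there would be discretionary. Renal repeats follow a value that already meets the hold criteria, and Protocol 6.3 also gives some placebo patients repeat renal testing. These points stand. They narrow the effect to higher thresholds and combined criteria, and for eGFR they make both its size and its arm imbalance uncertain.

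Third, adverse events of special interest are summarized with laboratory values listed (SAP 9.2.4), independently of windows. That is partial cover, but it does not replace the threshold counts.

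**Conclusion.** The conflict between SAP 6.7.5 and SAP 9.5 to 9.7 is real and should be corrected before database lock. As written, 6.7.5 removes repeat and unscheduled values from the liver-threshold and combined rows, the eGFR categories and declines, and time to elevation. The error runs one way, towards understating worst values or delaying first elevation. It falls mainly on thresholds such as >8×ULN and on combined criteria first met on a repeat. Time to elevation changes only if the first qualifying value comes from an unscheduled draw.

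The size cannot be computed. A reader might try to put a percentage on the lost >5× or >8× cases by modelling ALT curves, but the documents give no distribution of peaks, no rise or recovery times, no number of patients with repeats, and no share of peaks that fall between visits. They also do not say that peaks usually fall on repeats.

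The conclusion rests on two assumptions: that the general rule would be applied where no exception is written, and, for eGFR, that the categories are meant as worst values. If the eGFR categories are by-visit summaries, one record per window is appropriate there, and the SAP should say so.

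**What to change.** In SAP 6.7.5, limit the one-record rule to efficacy analyses and by-visit descriptive summaries.

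In SAP 9.5, state that the ALT/AST/bilirubin threshold and combined rows, the worst eGFR category and percent decline, the maximum-severity shift and the time-to-elevation outputs use every post-baseline value in the relevant study period: scheduled, unscheduled, repeat, early discontinuation and Follow-up. Keep the existing separation of values before and after transition to the active drug period. State whether any eGFR category table is by visit.

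The cost is two SAP sentences and a different record filter. The values are already collected. Reported event counts may rise slightly, which is the purpose of the change.
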